## 12.2 Central Laboratory

### 12.2.1 Plasma Pharmacokinetics

At sites participating in plasma sampling for PK analysis, approximately 245 patients randomized to the Pralatrexate Arm (two-thirds of the planned total) who consent to plasma sampling will have sampling performed at cycle 1, dose 1 (pre-injection, end of injection, and 8 and 24 hours post-injection). Of these 245 patients, 20 patients at select sites will also have plasma sampling performed at cycle 2, dose 3 (pre-injection, end of injection, and 8 and 24 hours post- injection).

Plasma samples will be split in 2 equal aliquots and frozen in separate tubes for analysis of pralatrexate concentration. The concentrations of pralatrexate at each time-point will be determined using validated bioanalytical methods at MPI Research. See Study Instructions provided by Allos/designee for detailed guidance regarding the collection, processing, and shipment of samples.

Standard PK parameters will be estimated from the limited plasma sampling (eg, area under the curve [AUC], maximum concentration [ $C_{max}$ ], and half-life [ $t_{1/2}$ ]), and POPPK analyses will be conducted via nonlinear mixed-effects modeling to estimate POPPK parameters for pralatrexate.

### 12.2.2 Independent Pathology Review

Confirmation of PTCL histopathology subtype will be performed by an independent pathology reviewer. Pathology specimens from the patient's initial diagnosis will be sent to independent pathology review. Confirmation of an eligible PTCL histopathology subtype must be documented by the independent pathology reviewer prior to randomization. See Study Instructions provided by Allos/designee for detailed guidance regarding sample requirements and the preparation and shipment of slides.

### 12.2.3 Medical Photography

Documentation of cutaneous disease with medical photography will be performed by the site at screening and at each response assessment, if applicable. Up to 5 target lesions will be chosen by the investigator and photographed. See Study Instructions provided by the central medical photography laboratory (Canfield Scientific, Inc.) for detailed guidance regarding photograph requirements and transfer.

### 12.2.4 Central Radiology Imaging

Radiologic imaging of each patient will be completed at screening and at each response assessment as described in [Sections 10.1](#) and [10.6](#). All scans will be sent to a designated, independent central reviewer until at least the first interim analysis. See Study Instructions provided by the central reviewer (CoreLab Partners) for detailed guidance regarding imaging requirements and transfer.

## 13 CONCOMITANT MEDICATIONS

All medications administered from 7 days prior to randomization through 30 days after the last pralatrexate administration, or through 30 days after treatment discontinuation criteria are met for patients in the Observation Arm, will be recorded on the CRF. Additions, deletions, or changes of dosage of medications will also be noted.

### 13.1 Antiemetic Therapy

There is no evidence to expect drug-drug interactions between pralatrexate and standard antiemetic therapy and no specific antiemetic therapy has yet been proven to be superior over others in the setting of pralatrexate administration. Therefore, prophylaxis and treatment of nausea and vomiting can be administered according to the standard of care within the institution; however, administration is not recommended prior to the first dose because of the low emetogenicity of pralatrexate.

Steroids are not allowed for prophylaxis or treatment of nausea/vomiting.

### 13.2 Hematopoietic Growth Factors

Hematopoietic growth factors may be administered in accordance with the instructions for treatment modification for hematological events in [Table 7.1](#). Erythropoietin will be allowed if it is judged by the investigator to be in the best interest of the patient (eg, for patients with underlying anemia or unacceptable hematologic toxicity). Other hematopoietic growth factors (eg, granulocyte colony-stimulating factor [G-CSF], granulocyte-macrophage colony-stimulating factor [GM-CSF]), with the exception of pegfilgrastim (Neulasta®, Amgen), are to be administered per package insert.

### 13.3 Mucositis Management

Patients receiving pralatrexate should be assessed for risk of mucositis prior to start of treatment with continued assessment for symptoms prior to each dose. Medications and mouthwashes, including salt and soda mouthwashes, used for prophylaxis and/or treatment of mucositis must be recorded as concomitant medications. Dose modifications for mucositis are found in [Table 7.2](#); however, investigators should refer to the National Comprehensive Cancer Network (NCCN) Task Force Report for the Prevention and Management of Mucositis in Cancer Care for assistance with risk assessment and grading of mucositis, guidance on symptom management, and patient education tools on effective oral care regimens and reporting of mucositis symptoms.

### 13.4 Corticosteroid Use

Patients are allowed to begin study treatment while receiving systemic corticosteroids provided the patient has been taking a continuous dose of  $\leq 10$  mg/day of oral prednisone or equivalent for at least 4 weeks or as part of a CHOP prednisone taper. Other concomitant systemic corticosteroid therapy during the pralatrexate treatment/observation phase of this

study is prohibited (with exception of corticosteroids administered for a non-lymphoma condition, eg, bronchitis, for  $\leq 10$  days). Inhaled or topical steroids (administered for reasons other than to treat cutaneous disease) are allowed.

### **13.5 Prophylactic Anti-infective Agents**

Use of prophylactic antibiotics/antivirals/antifungals is allowed and may be administered at the discretion of the investigator. If antibiotic prophylaxis is indicated, alternatives to sulfamethoxazole/trimethoprim must be considered as it has antifolate activity. Due to the possibility of additive toxicity (including myelosuppression) when used in combination with pralatrexate, concurrent use of the 2 drugs should be avoided.

### **13.6 Pain Management**

Pain management should be addressed promptly by the attending physician managing the patient. Due to the contribution of renal excretion (approximately 34%) to the overall clearance of pralatrexate, concomitant administration of non-steroidal anti-inflammatory drugs (NSAIDs) and probenecid may result in delayed clearance of pralatrexate. These drugs should be used with caution while patients are enrolled in this study; alternatives to NSAIDs and probenecid should be considered when possible.

### **13.7 Blood Products**

Blood product transfusions are allowed per the discretion of the investigator.

### **13.8 Other Supportive Care Medications**

The administration of appetite-stimulating hormones (eg, megestrol acetate) is allowed to control anorexia and cachexia.

### **13.9 Radiotherapy, Cytotoxic Therapy, Biologic Therapy, or Immune Response Modifiers**

No RT, other cytotoxic agents, biologic therapy, immune response modifiers, or stem cell transplant are to be administered to patients until pralatrexate/observation has been discontinued.

## 14 ADVERSE EVENTS

### 14.1 Definition

An AE is defined as any untoward medical occurrence in a patient or clinical investigation patient, temporally associated with the use of a medicinal product, whether or not considered related to the medicinal product. Therefore, an AE can be any unfavorable and unintended sign (including an abnormal laboratory finding), symptom, or disease (new or exacerbated) temporally associated with the use of a medicinal product. This definition of an AE will be extended in this study to include any untoward medical occurrence in patients participating in the Observation Arm of the study, as well.

The term “toxicity” is not clearly defined by regulatory organizations and is currently used only for historical reasons by the NCI. Therefore, the term “adverse event” is used throughout this document to refer to any unfavorable and unintended sign (including an abnormal laboratory finding), symptom, or disease temporally associated with the study drug, as well as any other study-treatment-related toxicities. However, since this is an investigational study, all toxicities are considered AEs and must be reported.

Examples of an AE **include**:

- Exacerbation of a chronic or intermittent pre-existing condition including either an increase in frequency and/or intensity of the condition.
- New conditions detected or diagnosed after investigational product administration, even though it may have been present prior to the start of the study.
- Signs, symptoms, or the clinical sequelae of a suspected drug interaction.
- Signs, symptoms, or the clinical sequelae of a suspected overdose of either investigational product or a concurrent medication.
- AEs may include pre-treatment or post-treatment events that occur as a result of protocol-mandated procedures (ie, invasive procedures, modification of patient’s previous therapeutic regimen).

Examples of an AE **do not include** a/an:

- Medical or surgical procedures (eg, endoscopy, appendectomy); the condition that leads to the procedure is an AE.
- Situations where an untoward medical occurrence does not occur (eg, social and/or convenience admission to a hospital).
- Anticipated day-to-day fluctuations of pre-existing disease(s) or condition(s) present or detected at the start of the study that do not worsen.

## 14.2 Guidelines for Recording and Attribution Scoring of Adverse Events

Timely and complete reporting of AEs is essential. Monitoring and documentation of all AEs allows for identification of potential study-drug or dose-related AEs, and for adherence to regulatory requirements. Please refer to the CRF Completion Guidelines located in the study binder for detailed instructions.

### 14.3 Recording of Adverse Events

#### 14.3.1 Recording of Adverse Events

Any AE that occurs from the time the study IC is obtained until randomization needs to be recorded on the AE CRF page(s), **only** if the event was related to a study procedure. All other AEs/findings prior to randomization must be recorded as baseline findings on the applicable CRF page(s).

Any AE that occurs from randomization through 30 days after the last dose of pralatrexate or through 30 days after treatment discontinuation criteria are met for the Observation Arm must be recorded on the AE CRF. From 31 days after the last dose of pralatrexate, only AEs that are related to pralatrexate need to be captured on the AE CRF.

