### 7.3 Study Duration

Patients will receive study treatment (pralatrexate or observation) until one of the criteria listed below for study treatment discontinuation applies:

- Development of PD
- Initiation of radiation therapy (RT) or systemic chemo/biological therapy for treatment of PTCL
- Receipt of systemic steroids for > 10 days, with the exception of those as stated in exclusion criterion #5 (see [Section 8.4](#))
- Development of an AE that interferes with the patient's participation
- Lost to follow-up
- Patient decision
- Investigator decision
- Sponsor decision

In addition, for those patients randomized to the Pralatrexate Arm, additional pralatrexate treatment discontinuation criteria are:

- 3 or more consecutive doses of pralatrexate omitted or more than 28 days between doses of pralatrexate
- Treatment with pralatrexate for 2 years

All patients who receive at least 1 dose of pralatrexate will be followed for safety through 35 ( $\pm$  5) days after their last dose of pralatrexate or until all treatment-related AEs have resolved or returned to baseline/Grade 1, whichever is longer, or until it is determined that the outcome will not change with further follow-up.

Patients who are randomized to the Observation Arm who do not discontinue the study within 3 days of randomization will be followed for safety until 35 ( $\pm$  5) days after study treatment discontinuation criteria are met.

All patients who are randomized will be followed until objectively documented PD for up to 7 years from randomization. The details of response follow-up are provided in [Section 10.8](#). PD will be confirmed by central review until the first PFS analysis, see [Section 15.6.1](#), and per investigator assessment thereafter. Subsequent therapies for PTCL will be collected for up to 7 years from randomization; the best response to the first subsequent therapy will be collected. Survival follow-up will continue for up to 7 years from randomization.

As discussed in [Section 15.6.1](#), an analysis will be performed when both 280 PFS events and 128 OS events have occurred. If the PFS analysis is not significant at the 0.05 level, the study will be stopped.

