### **14.6.2 Serious Adverse Event Reporting**

- Any SAE that occurs from the time the study IC is obtained until randomization needs to be reported only if the event was related to a study procedure.
- Any SAE that occurs from randomization through 30 days after the last dose of pralatrexate or through 30 days after treatment discontinuation criteria are met for the Observation Arm must be reported to Allos within 24 hours of knowledge of the event. From 31 days after the last dose of pralatrexate, patients will continue to be assessed for SAEs that are related to pralatrexate.

- SAEs (regardless of causality) must be reported and the SAER faxed **within 24 hours of knowledge of the event to:**

Allos Therapeutics, Inc.  
Primary Contact: Clinical Drug Safety and  
Pharmacovigilance Department  
Phone: [REDACTED]  
Fax: [REDACTED] or [REDACTED]  
Email: [contact]

Allos may request additional information from the investigator to ensure the timely completion of accurate safety reports. Safety data that are critical to the reportability of an SAE, such as causality assessment and serious criteria, should be included in the initial fax for SAER. If omitted, a timely response to drug safety data queries received from Allos or an Allos designee is expected.

The investigator must take all therapeutic measures necessary for resolution of the SAE. Any medications necessary for treatment of the SAE must be recorded onto the concomitant medication section of the patient's CRF.

SAEs that are pralatrexate-related will be followed until resolution or returned to baseline/Grade 1, whichever is longer, or until it is determined that the outcome will not change with further follow-up.

Additionally, the SAE must be entered on the AE page(s) of the CRF. Follow-up SAERs need to be submitted to Allos as soon as additional information regarding the event becomes available (eg, diagnosis is made, laboratory or test results, event course, outcome, etc). The Allos CRA or designee will collect the original SAER from the site.

Allos/designee will be responsible for reporting SAEs to the regulatory authorities in accordance with applicable expedited reporting regulatory guidelines. The investigator is responsible for submitting SAEs to his/her Institutional Review Board (IRB)/Ethics Committee (EC)/Research Ethics Board (REB).

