Patients will be followed for safety until 35 (\pm 5) days after the study treatment discontinuation criteria are met. Patients will be followed to determine time to progressive disease (PD) and survival for up to 7 years from randomization or until 35 (\pm 5) days after the last dose of pralatrexate, whichever is longer. Patients who withdraw from treatment prior to PD without withdrawing consent will be followed for disease status whenever possible, even if subsequent therapy, including transplant, has been initiated prior to documented PD per central review, at least until the first interim analysis.

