PFS time is calculated as the number of days from randomization to the date of objective documentation of PD or death, regardless of cause (PD date/death date - date of randomization + 1). Patients who are alive without a disease response assessment of PD will be censored at their last disease assessment date or the date of randomization, whichever is later. Date of progression will not be imputed for patients with missing tumor assessment(s) before an assessment of PD. Patients who withdraw from treatment prior to PD without withdrawing consent will be followed for disease status whenever possible, even if subsequent therapy, including transplant, has been initiated prior to documented PD per central review at least until the first interim analysis. Patients who have not died and who have no response assessments after baseline will be censored at randomization.

Overall Survival Time

OS time is calculated as the number of days from randomization to death (date of death - date of randomization + 1). Patients who have not died (no record of death) or are lost to follow-up will be censored at the date of last contact. Patients who withdraw from study visit participation will be followed for survival status. OS will be reported in months.

Treatment-emergent Adverse Event

A treatment-emergent AE is defined as an AE that occurs on or after study day 1 and that is a higher grade than was present just prior to study day 1.

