8.6 Safety Analyses

Analysis of safety will be performed on the safety analysis set. Study data will be monitored on an ongoing basis by the clinical study team including the medical monitor and the clinical drug safety team's routine activities to ensure patients' safety.

Adverse Events

The Medical Dictionary for Regulatory Activities (MedDRA) will be used to code all AEs to a system organ class (SOC) and a preferred term. Patient incidence of AEs will be tabulated by SOC, preferred term, and severity grade for all treatment-emergent AEs, serious adverse events (SAEs), treatment-related AEs, and treatment-related SAEs. Each of these outputs will include tabulation by maximum severity for each SOC and preferred term as reported by the investigator based on Common Terminology Criteria for Adverse Events (CTCAE),

Version 4.0. If an AE cannot be graded based on CTCAE, the investigator will assign a severity based on 1 = mild, 2 = moderate, 3 = severe, 4 = life threatening, and 5 = Death related to AE. Summaries of AEs that are treatment-emergent, SAEs, treatment-related AEs, and treatment-related SAEs occurring in at least 5% of the patients will be provided in descending order of frequency by SOC and preferred term.

Additional tables summarizing patient incidence (by preferred term) of the following will be generated:

- All AEs;
- SAEs;
- Treatment-related AEs;
- Treatment-related SAEs;
- Grade 3 or higher AEs;
- AEs leading to the discontinuation of pralatrexate or removal from study;
- AEs leading to dose reductions of the study drug;
- AEs with incidence $\geq 5\%$; and
- Deaths.

Adverse Events Grouped by Similar Preferred Term

Summary tables of treatment emergent, treatment-related, serious, and serious treatment-related AEs grouped by similar preferred term will be presented. For this presentation, certain similar preferred terms were identified and coded to the same preferred term in order to present the event in a uniform manner. Terms are presented in [Table 11.1](#) of Appendix 11.4 (additional preferred terms may be identified within each category during data review and added to this list).

Separate outputs will be provided for subgroups defined by age group (< 65 and ≥ 65), gender, and race (if feasible).

Detailed listings for all AEs and listings and/or narratives will be provided for serious and significant AEs and deaths (with “on-study” deaths [deaths that occur before the end of safety follow-up period] identified).

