9 LIST OF PLANNED TABLES, FIGURES, LISTINGS, AND APPENDICES

Table, listing, and figure shells will be created prior to the final analysis and will include information regarding the structure of each output. The following tables (Table 9.1), listings (Table 9.2), and figures (Table 9.3) could be provided.

Table 9.1. Planned Tables

Title	Description
Patient Disposition – FAS	Tabulates the disposition of all patients, including the number of patients randomized, the number of patients who receive protocol-specified treatment, the number of patients who were randomized and never received protocol-specified treatment. The reason for protocol-specified treatment discontinuation and the reason for study discontinuation will also be summarized. Long-term follow-up will be summarized based on the most recent assessment (alive, dead, lost to follow-up, consent withdrawn).
Baseline Demographics – FAS	Tabulates summary statistics of the demographics (gender, race, age, geriatric age group < 65, ≥ 65).
Baseline Characteristics – FAS	Tabulates baseline disease characteristics.
Patient Accountability – FAS	Tabulates the number of patients within each analysis set and the reason for exclusion from each analysis set.
Pralatrexate Administration – FAS (Pralatrexate Arm)	Summarizes the total number of cycles started, the number of doses received, duration of treatment, the cumulative dose of treatment, the number and percentage of patients with modifications by type of dose modification and reason for the dose modification. The number of dose reductions/omissions/delays per patient will also be summarized.
PFS – FAS	Summary of PFS results including median (95% CI) PFS time by treatment arm, HR (95% CI), and log-rank P value. PFS estimates (95% CIs) from K-M curves at specific time points (eg, 6-month intervals).
OS – FAS	Summary of OS results including median (95% CI) survival time by treatment arm, HR (95% CI), and log-rank P value. Survival estimates (95% CIs) from K-M curves at specific time points (eg, 6-month intervals).

Title	Description
Objective Response Rate – FAS	Summary of ORR results
Subsequent Therapy – FAS	Summary of number of patients receiving subsequent therapy, including stem-cell transplant, and timing of subsequent therapy. Also includes response status when subsequent therapy was received.

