ECOG Performance Status – Safety Analysis Set	Summary of ECOG performance status results at each scheduled time-point and the change from baseline.
Concomitant Medications – Safety Analysis Set	Summary of administered concomitant medications by ATC code and preferred term.

FAS = full analysis set HR = hazard ratio SOC = system organ class
PFS = progression-free survival K-M = Kaplan Meier SAE = serious adverse event
OS = overall survival ORR = objective response rate ATC = Anatomical Therapeutic Chemical
CI = confidence interval AE = adverse event ECOG = Eastern Cooperative Oncology Group

Table 9.2. Planned Listings

Title	Description
Patient Accountability	Listing of all patients and the analysis set inclusion information.
Patient Withdrawal	Listing of all patients who withdraw from the study, including the reason for withdrawal and the time of withdrawal.
Protocol-specified Treatment Administration	Listing of all patient protocol-specified treatment administration information.
Adverse Events	Listing of all reported AEs by patient.
Serious Adverse Events	Listing of all patients with at least 1 reported SAE. Only the AEs identified as serious will be included. Listing will include patient number, SOC, and preferred term of AE, date of onset, date of resolution, CTCAE Grade, action taken, and outcome.
Deaths – Safety Analysis Set	Listing of deaths that occur within 30 days of the last dose of protocol specified treatment, including cause of death.
Adverse Events Leading to Protocol-specified Treatment Discontinuation	Listing of all patients who discontinue protocol-specified treatment due to an AE. The listing will include the AE, date of onset of the AE, date of resolution of the AE, severity of AE, and the CTCAE severity grade of the AE.
Hematology	Listing of all hematology parameters.
Serum Chemistry	Listing of all serum chemistry parameters.
Electrocardiograms	Listing of all ECG results, including heart rate, QRS, PR, QT, and QT _c intervals.
Concomitant Medications	Listing of all concomitant medications including the ATC code and preferred term.
ECOG Performance Status	Listing of ECOG performance status at each assessment.
Lesion Measurements	Listing of all lesions at each time-point, including the sum of all target lesions and change from baseline and percent change from baseline.
Efficacy Parameters	Listing of all efficacy parameters for each patient, including survival time, objective response, and PFS time.

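### AE percentages are to be compared by arm with no account of AE observation time, which is likely to differ between arms by an unknown amount and in an unknown direction

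*Protocol*

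**What the plan says.** **When capture ends.** Protocol 14.3.1 has AEs recorded, once a patient is randomized, "through 30 days after the last dose of pralatrexate or through 30 days after treatment discontinuation criteria are met for the Observation Arm". Protocol 14.6.2 uses the same two anchors for serious events, the second of them for observation: "Any SAE that occurs from randomization through 30 days after the last dose of pralatrexate or through 30 days after treatment discontinuation criteria".

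**What ends study treatment.** Protocol 11.1 lists eight criteria for both arms, including progression. For the Pralatrexate Arm it adds a rule on omitted doses or a long gap between doses, and a 2-year limit. The same section lets pralatrexate continue beyond 2 years by agreement with the sponsor. Protocol 10.5.2 and 10.5.3 and SAP 3 also limit observation contacts to 2 years, although 11.1 does not list this as a stopping criterion for observation.

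**What is tabulated.** SAP 8.6: "Patient incidence of AEs will be tabulated by SOC, preferred term, and severity grade for all treatment-emergent AEs". The AE tables in SAP Table 9.1 are laid out by treatment group. Treatment duration appears only in the Pralatrexate Arm administration table: "Summarizes the total number of cycles started, the number of doses received, duration of treatment, the cumulative dose of treatment". The only time-based safety analysis is the Cox model for B-symptoms and pruritus.

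**Where the analysis window ends.** SAP 5.2 gives a start but no end: "A treatment-emergent AE is defined as an AE that occurs on or after study day 1". SAP 11.3 sets post-treatment cutoffs from a treatment stop day that it does not define for observation. One planned listing for the safety set (SAP Table 9.2) is a "Listing of deaths that occur within 30 days of the last dose of protocol specified treatment, including cause of death"; observation patients have no dose.

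**The concern.** A crude percentage depends on both the event rate and the time over which events are recorded. Here that time is set by rules that differ between arms and by PFS, which the drug is intended to change.

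- The last-dose anchor and the dose-omission rule shorten all-cause capture on pralatrexate.
- A PFS benefit lengthens it, because progression closes the window in both arms.

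Safety is the only stated secondary objective. The AE tables carry no test, but they will be read side by side. Without AE observation time for both arms, a reader has only indirect clues (disposition, PFS curves) to how much of a difference is drug effect and how much is time under observation. Less frequent events are the most exposed: background illness, grade 3 or higher events and serious events.

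**Working it through.** **The plan's own figures.** The documents give no AE observation time to reproduce. The PFS inputs can be checked. With 280 events, HR 0.67 and 2:1 allocation, √(280 × 2/9) × |ln 0.67| − 1.96 = 7.89 × 0.400 − 1.96 = 1.20, which is 88.5% power and agrees with the stated minimum of 80%.

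**Inputs from the documents.** Observation median PFS 10 months, exponential, and HR 0.67 (SAP 3.2); a 30-day tail (Protocol 14.3.1), taken as 1 month; a 24-month cap, applied to both arms.

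**Assumptions, shown as ranges.**
- Equal true AE rate r in both arms: 0.03 to 0.10 per month.
- Excess non-progression stopping on pralatrexate s: 0 to 0.05 per month. Negative values were not examined.
- Lag from last dose to the stopping criterion: 0 to 28 days.

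**Formulas.** The observation stopping rate is ln 2/10 = 0.0693 per month, with W = min(T, 24) + 1. The pralatrexate rate is HR × 0.0693 + s, with W = max(0, min(T, 24) − lag) + 1. Crude incidence is 1 − E[exp(−rW)]. At lag 0 with stopping rate λ,

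E[exp(−rW)] = exp(−r) × {λ/(λ+r) × (1 − exp(−24(λ+r))) + exp(−24(λ+r))}.

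**Worked cases, r = 0.03, lag 0.**
- Observation (λ = 0.0693): 1 − 0.9704 × 0.7258 = 29.6%.
- Pralatrexate, HR 0.67, s = 0 (λ = 0.0464): 1 − 0.9704 × 0.6702 = 35.0%. Ratio 29.6/35.0 = 0.85.
- Pralatrexate, HR 0.67, s = 0.05 (λ = 0.0964): 1 − 0.9704 × 0.7741 = 24.9%. Ratio 29.6/24.9 = 1.19.

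**Results.** The mean window on observation is 12.7 months. Ratios are observation/pralatrexate over r = 0.03 to 0.10.

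| Scenario | Lag (days) | Mean pralatrexate window (months) | Crude ratio |
|---|---|---|---|
| Anchor alone (HR 1, s = 0) | 7 | 12.5 | 1.01–1.02 |
| Anchor alone (HR 1, s = 0) | 14 | 12.2 | 1.03 |
| Anchor alone (HR 1, s = 0) | 28 | 11.8 | 1.06–1.07 |
| Planned PFS effect, s = 0 | 0 | 15.5 | 0.85–0.89 |
| Planned PFS effect, s = 0 | 28 | 14.6 | 0.89–0.93 |
| Planned PFS effect, s = 0.05 | 0 | 10.3 | 1.12–1.19 |
| Planned PFS effect, s = 0.05 | 28 | 9.5 | 1.21–1.29 |

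**Break-even.** With the planned PFS effect the ratio is 1.00 at s = 0.023 (lag 0), 0.017–0.018 (14 days) or 0.013–0.014 (28 days). As excess stopping by 12 months, 1 − exp(−12s), that is 14% at 0.013 and 24% at 0.023. At s = 0.05 it is 45%.

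**Frequent toxicity.** At 0.5 events per month, crude incidence stays between 86% and 95% throughout.

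**What adjustment achieves.** In a simulation of 1,000,000 patients per arm, the exposure-adjusted ratio was 0.997–1.005 when stopping was independent of AE risk; the constant hazard guarantees this. With a gamma frailty (variance 0.5, assumed) acting on both AE rate and s, at s = 0.05, it was 1.07–1.13 against a crude 1.11–1.35. At s = 0.023, lag 0, it was 1.05–1.06 against a crude 1.00–1.03.

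**The case against.** The strongest reply is that crude incidence is a legitimate descriptive measure, no AE test is planned, and the main drug toxicities barely move. The recording rule contributes little by itself. The larger shifts need either the planned PFS benefit, which is not a fault of the recording rules, or s = 0.05 per month, which has no source in the documents. Most non-progression criteria are shared, and in an open-label trial they could also end observation sooner. All of this stands, and it limits the point to a missing display.

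Three stronger inferences are tempting, and the documents do not support them.

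- **That the 2-year limit is a second rule shortening pralatrexate capture.** Protocol 10.5.2 and 10.5.3 and SAP 3 cap observation contacts at 2 years too, and 11.1 allows pralatrexate to continue. It should not be counted as a clear asymmetry.
- **That late related-only events are added on pralatrexate alone.** Protocol 14.3.1 reads that way, and Appendix 2 shows no AE entry at post-treatment follow-up for observation. But Protocol 10.8 asks for study-treatment-related AEs at each follow-up of all randomized patients. The text is unclear rather than one-armed.
- **That equal true rates must give different percentages, or must flatter pralatrexate.** At break-even the ratio is 1.00, and with the PFS benefit alone it goes the other way.

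Deaths are also partly covered elsewhere: SAP 8.6 plans a deaths table and identifies on-study deaths by the end of safety follow-up, which works in both arms. An observation stop day can be inferred from Protocol 11.1, although SAP 11.3 does not state it.

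**Conclusion.** The point holds as a cheap improvement, not as an error that invalidates the safety analysis. AE observation time is likely to differ by arm, the plan neither summarises it for observation nor adjusts for it, and the end of the analysis window is not fixed.

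Under the planned PFS effect and equal true AE rates, the crude ratio could lie anywhere from about 0.85 to about 1.29. That range rests on the assumed AE rates, lags and excess stopping; it is an illustration and not a bound. The documents give no non-progression stopping rate, so neither the size nor the sign of the net effect can be determined in advance.

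**What to change.** In SAP 8.6, beside the crude tables:

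1. Summarise AE observation time in both arms.
2. Add exposure-adjusted incidence by arm (patients with an event per patient-year at risk, 95% CI) for all-cause, grade 3 or higher and serious AEs. Cumulative incidence of first AE at common times, such as 3, 6 and 12 months, is an optional extra.
3. State the end of the treatment-emergent window in each arm, including the stop day for observation. Use it for the death listing in Table 9.2, and keep late events captured under a related-only rule out of all-cause comparisons.

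Three sets of passages need reconciling:
- SAP 3 anchors safety follow-up on discontinuation criteria for all patients. The Protocol Synopsis and 7.3 anchor it for pralatrexate at 35 (± 5) "days after their last dose of pralatrexate or until all treatment-related AEs have resolved" or returned to baseline or Grade 1, whichever is longer.
- Appendix 2 footnote 12 ends observation AE recording when criteria are met; Protocol 10.7.2 and 14.3.1 end it 30 days later.
- Protocol 10.8 and 14.3.1 with Appendix 2, on late related events.

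**Cost.** SAP wording and a few extra tables from data already collected. The rates assume a roughly constant hazard. Adjustment does not fully remove bias when stopping is related to AE risk, and near break-even it can sit slightly further from 1 than the crude ratio. It also does not correct for denser AE recording: three dosing visits per 4 weeks on pralatrexate against one visit and one contact on observation. Both displays should therefore be shown.
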